## 2. Patient Identification

Clinic staff will prospectively identify patients ages 50 to 75 with an abnormal fecal test (FIT) result. A preadjudication process will be completed to confirm eligibility for all patients by the patient navigator and a clinical team (including the study gastroenterologist).

Patients will be excluded if they have had a recent negative colonoscopy (within the past 3 years) or have a limited set of health conditions (e.g. metastatic cancer, on hospice or in a nursing home, end-stage renal disease, home oxygen use).

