## 3. Randomization and blinding

Patients meeting clinical eligibility criteria will be randomized by the health center (Sea Mar) analyst to receive either the patient navigation intervention or usual care. Study identification numbers linked to patients will be uploaded into REDCap® on a weekly basis, for patients in the navigation arm, with date of abnormal FIT result. We anticipate that the time between patient identification and study randomization will take about 2 weeks. (See **Handling of Deviations and Protocol Amendments 9.4**)

Randomization will be performed using a stratified approach that considers patients' county of residence. We will use Sealed Envelope (London, UK) to randomize patients 1:1 to navigation or usual care in blocks of 4 to 8 individuals, stratified on county of residence. For practical reasons, neither the research team nor the clinic staff will be blinded to randomization assignment. However, measures have been taken to preserve as much blinding as possible. Staff trained in navigation will not perform colonoscopy referral coordination (as part of usual care). Patients randomized to patient navigation are removed from the referral coordinator list to eliminate potential outreach by referral coordinators. In this way, the patient navigation intervention will not be overlaid on usual care, as doing so would result in multiple contacts from multiple clinic staff. (Consistent with usual care, referral

coordinators will contact referred patients who have not completed a colonoscopy making up to three phone attempts; patients who are not reached will be sent a letter.)

The randomization will result in 600 patients assigned to the patient navigation arm and 600 assigned to the usual care arm. We will assess rates of colonoscopy receipt at 1 year overall, and will perform a heterogeneity of treatment effect analysis to assess differential effects by age, sex, ethnicity, language preference, insurance status, and probability of adherence (based on the risk model), using data from the electronic health record.

CHR analysts will assign a colonoscopy completion probability, based on the risk prediction model. These methods have been described previously.

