## 5. Study outcomes

## 5.1. Outcome variables

Primary and secondary outcomes and process measures are displayed in Table 1.

Primary outcome: Our primary outcome is whether patients obtain a follow-up colonoscopy within 1 year of having an abnormal FIT result, as assessed through chart audit. Because the navigator's role involves tracking completed colonoscopies and communicating colonoscopy results to patients, it is likely that navigated patients will have more complete capture of colonoscopy events (our primary outcome) than usual care patients. To minimize bias in the collection of primary outcome data across study arms, the study team will implement an adjudication process, where systematic chart abstraction and medical records requests to referring gastroenterologists (GIs) will be performed by an abstractor who is blinded to study arm assignment (See Section 6 below). Starting after the 1-year evaluation interval, procedure and pathology reports from all study patients without electronic health record-evidence of a completed colonoscopy will be requested, and adjudicated by the project chart auditor; the GI and clinical champion will be consulted as questions arise.

Secondary outcomes include time to colonoscopy receipt and adequacy of bowel preparation (% adequate). We will also report colonoscopy outcomes (N, % adenomas and advanced adenomas detected; n cancers found). (See Handling of Deviations and Protocol Amendments 9.3)

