#### 8. Handling of Deviations and Protocol Amendments

- 8.1. Included all patients ages 50-75 with an abnormal FIT result, eliminated requirement of having moderate or high risk of follow-up colonoscopy non-adherence. Given the relatively low colonoscopy completion probability in the highest quintile group (65% vs. 93% estimated), we plan to randomize all eligible abnormal FIT patients. We will still prospectively calculate the patients' estimated probability of obtaining a colonoscopy, using the risk prediction model and preform subgroup analysis considering risk level as a moderator of effectiveness.
- 8.2. Eliminated cost and cost-effectiveness analysis. These analyses were eliminated because of COVID-19 resources constraints; through an official request to NCI dated 3/1/2021.
- 8.3. Eliminated no show/canceled appointments as a secondary outcome. We eliminated as an outcome noshow/canceled appointments because the number of referring GI practices would lead to inconsistencies and inaccuracies in the collection of these data.
- 8.4. Changed the randomization process. Following an electronic health record conversion, the original automated randomization in place at the partnering health center was disabled. As a result, from August 2021 through April 2022, patients were randomized weekly using the SURVEYSELECT procedure in SAS (Cary, NC).
- 8.5. Used Restricted Mean Survival Time for time-to-event analysis. To assess differences in time to colonoscopy completion between study arms (secondary outcome), we originally planned to use Cox proportional hazards and median survival time. Instead, we computed the log-rank test and restricted mean survival time (adjusted for county). Restricted mean survival time provides estimates of the mean time to event regardless of event rate whereas conventional median survival time is only computable when the event rate is 50% or greater. Moreover, restricted mean survival time is a more direct and interpretable measure of actual survival time, compared to a hazard ratio derived from a Cox model.
- 8.6. Added county and eliminated Hispanic ethnicity as potential moderators. County (8 unique counties in WA State) was added as a potential moderator, given possible variation by county in GI provider waittimes and other factors. We also eliminated Hispanic ethnicity as a moderator as it has a strong correlation with preferred language.

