- 8.7. Added two sensitivity analyses to account for COVID-19-related care suspensions. Given possible impacts of COVID-19-related care suspensions, we performed a sensitivity analysis that assessed colonoscopy completion at 3 months, 6 months, 9 months, 12 months and 18 months following an abnormal FIT result. Additionally, we report number of completed colonoscopy every 3-months throughout the recruitment and evaluation intervals (July 2019 through December 2022).

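### The quarterly colonoscopy count in SAP 8.7 has no denominator, so it cannot size a partial fall or recovery in care, or separate it from slower enrolment

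*SAP*

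**What the plan says.** SAP 8.7 is headed "Added two sensitivity analyses to account for COVID-19-related care suspensions". The first of the two analyses "assessed colonoscopy completion at 3 months, 6 months, 9 months, 12 months and 18 months following an abnormal FIT result". It runs on each patient's own clock and pools all calendar periods. For the second, the SAP states that "we report number of completed colonoscopy every 3-months throughout the recruitment and evaluation intervals (July 2019 through December 2022". This is the only one of the two on calendar time. The SAP gives it no denominator, arm split, suspension dates, model or comparison.

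Three other places determine how many patients could contribute to a given quarter:

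- Entry is staggered. SAP section 2 states that "Clinic staff will prospectively identify patients ages 50 to 75 with an abnormal fecal test (FIT) result".
- The primary outcome in SAP 5.1 is "whether patients obtain a follow-up colonoscopy within 1 year of having an abnormal FIT result, as assessed through chart audit". SAP 8.7 does not say whether the quarterly count stops at 12 months, and its companion analysis runs to 18.
- The last randomization date named is in SAP 8.4: "from August 2021 through April 2022, patients were randomized weekly using the SURVEYSELECT procedure". Neither document states when recruitment closed.

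**The concern.** The number of colonoscopies in a quarter is the number of patients still waiting multiplied by the rate at which they are scoped. A care suspension acts on the rate. A count moves with both. Under staggered entry the number waiting grows over roughly the first year, and April to June 2020, the fourth quarter of the series, falls within that growth. A reader who takes the preceding quarters as the pre-pandemic level uses a baseline that was still rising.

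Enrolment was itself probably disturbed. The Protocol Modifications table contrasts the planned timeline with pandemic interruptions and says the recruitment interval was extended to get nearer to 1,200. A count cannot separate fewer patients entering from less care for those already in, which is what an analysis of care suspensions needs to do. At stake is how a descriptive COVID-19 table is interpreted, not the treatment comparison.

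**Working it through.** The plan gives no figure for this series to reproduce. The check asks what the counts would look like under known conditions.

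**Inputs from the documents.** "The randomization will result in 600 patients assigned to the patient navigation arm and 600 assigned to the usual care arm" (SAP section 3); 12-month completion of 44% under usual care and 53.2% under navigation (SAP section 4, the smaller of its two detectable differences); 14 quarters from July 2019 to December 2022.

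**Assumptions.** Uniform entry over 34 months (to April 2022; 42 months also run). Follow-up of 12 months (18 also run). Constant hazard, or a front-loaded one with cumulative hazard −ln(1−p)·(t/12)^0.7. Suspension and pause dates are illustrative, as the documents give none.

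**Formulas.** Entry per arm is a = 600/34 = 17.65 per month. The constant hazard is λ = −ln(1−p)/12, which gives 0.0483 (p = .44) and 0.0633 (p = .532) per month.

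- First quarter, per arm: a·[3 − (1 − e^(−3λ))/λ]. This gives about 3.7 and 4.7, in total 8.4. The stepwise calculation used below gives 8.5; the difference is step width.
- Plateau, once entries and exits balance: 3a·(.44 + .532) = 52.94 × .972 = 51.5.

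**No pandemic effect, constant hazard**

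| Quarter | Count | Patient-months | Rate per 100 |
|---|---|---|---|
| 2019 Q3 | 8.5 | 152 | 5.57 |
| 2019 Q4 | 23.4 | 421 | 5.56 |
| 2020 Q1 | 36.1 | 650 | 5.55 |
| 2020 Q2 | 46.7 | 843 | 5.55 |
| 2020 Q3 to 2022 Q1 (each) | 51.5 | 928 | 5.54 |
| 2022 Q2 | 47.6 | 859 | 5.54 |
| 2022 Q3 | 32.7 | 591 | 5.53 |
| 2022 Q4 | 19.4 | 350 | 5.52 |

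The rise is 51.5/8.5 = 6.1-fold. With the front-loaded hazard it is 51.5/14.6 = 3.5-fold. Both come from the risk set alone.

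**The late fall depends on unstated inputs.** As tabulated it is (51.5 − 19.4)/51.5 = 62%. With 18-month follow-up it is (66.7 − 34.6)/66.7 = 48%. With entry continuing to December 2022 there is none: counts rise from 6.9 to 41.7 and stay there.

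**Changes in care or in entry (constant hazard unless stated)**

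| Scenario | 2020 Q1 | 2020 Q2 | 2020 Q3 |
|---|---|---|---|
| No effect | 36.1 | 46.7 | 51.5 |
| Hazard halved in Q2 | 36.1 | 24.3 | 54.6 |
| Complete stop in Q2 | 36.1 | 0 | 58.0 |
| No entry in Q2, care unchanged | 39.6 | 42.0 | 40.0 |
| Same pause, front-loaded hazard | 44.2 | 36.8 | 39.4 |

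In the halved scenario the rate goes 5.55, 2.78, 5.55. Read from counts, the drop is (36.1 − 24.3)/36.1 = 33% instead of 50%. The next quarter stands 54.6/36.1 = 1.51 times the pre-suspension level, although the rate has only returned to where it was. In the last row the count falls by (44.2 − 36.8)/44.2 = 17% with no change in care.

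**Is a crude rate enough?** No. With the front-loaded hazard and no pandemic effect, the rate runs 10.11, 7.66, 6.67, 6.10, then 5.89 on the plateau, and ends at 4.24. The first four quarters alone show a 40% decline ((10.11 − 6.10)/10.11), because early quarters hold mostly patients soon after their FIT and late quarters hold few of them.

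**The case against.** The strongest reply is that the series still shows something. A reader might infer from the missing denominator that the counts can reveal nothing about care suspensions. The calculation does not support that. A complete stop gives 36.1, 0, 58.0. Even a halved rate breaks a rising trend: 36.1, then 24.3 where 46.7 was expected, then 54.6. It is true that 24.3 is close to the 23.4 of October to December 2019, but the adjacent quarter is the natural comparison, and against it the dip is plain. This part of the reply stands. What is lost is the size of the dip, its cause and the size of the recovery.

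A reader might also infer that the series must show a false decline in late 2022. That needs recruitment to have closed before December 2022. The SAP's reference to separate recruitment and evaluation intervals and the April 2022 date suggest it, but neither document says so. The depth of any fall also depends on a follow-up limit that SAP 8.7 does not set.

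Finally, the item is descriptive: there is no test, estimate or decision rule. Under concurrent 1:1 randomization both arms should share nearly the same entry pattern, so nothing here supports a claim that the between-arm comparison, the primary outcome or the restricted mean survival time analysis is biased. That also stands, and it limits the weight of the point. It does not supply the missing denominator, and neither does the companion analysis, which pools calendar time.

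**Conclusion.** The point holds as a correction to a supportive, descriptive analysis. A raw quarterly count under staggered entry rises 3.5- to 6-fold through accrual alone. It shows a halving of care as a one-third fall and a return to normal as a 50% excess, and an enrolment pause can resemble reduced care. These sizes rest on uniform entry of 1,200 patients, the SAP's planning completion rates, 12-month follow-up and assumed suspension dates. Actual accrual was probably uneven, so the figures are illustrative. The early build-up appears in every scenario run, whereas the late fall is conditional on when recruitment closed. The primary analysis is unaffected.

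**What to change.** In SAP 8.7, replace the bare count with the following, for each calendar quarter and arm:

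- The number of colonoscopies and the patient-months at risk, counted from the FIT date to the first of colonoscopy or the end of the counted follow-up window. State that window.
- Both quantities split by time since FIT (for example 0–3, 3–6 and 6–12 months), because a crude rate drifts when completion is front-loaded.

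Add 12-month completion by quarter of the abnormal FIT, by arm. State the date recruitment closed, and mark the suspension dates on the series.

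FIT and colonoscopy dates are already needed for the time-to-colonoscopy outcome, so the cost is a few sentences in the SAP and a little code. There are small drawbacks. The table is longer and its early cells are sparse. The split reduces the drift but leaves some in the first and last quarters. The entry-cohort table spreads a short suspension over about four cohorts, so it complements the quarterly rates and does not replace them.
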